7.0 DATA MONITORING FOR SUBJECT SAFETY

Aim 1. PROCESS EVALUATION. There is no data monitoring for clinician and Veteran Advisory Council members subject safety as this is a study regarding work practices and is minimal risk to the clinicians.

Aim 2. NUDGE EFFECTIVENESS. These are not experimental therapies, and DSMB is not required. SGLT2 inhibitors and MRAs are HF medications prescribed in routine standard of care and are guideline-recommended.

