8.0 DATA ANALYSIS & STATISTICAL CONSIDERATIONS

Power calculation. One study reported a 14% absolute increase in beta-blocker prescription with enhanced alert compared to usual alert/usual care. Another reported a 7% absolute increase in new prescription of any GDMT in 30 days, also driven by beta-blocker. We anticipate a 5% absolute increase in new prescriptions (SGLT2 or MRA) per intervention arm, compared to usual care. We are anticipating a lower treatment effect because SGLT2 inhibitors are newer, potentially seen as requiring interdisciplinary collaboration, and MRAs require serial lab monitoring. To detect this difference with an 80% power and alpha of 0.05, a sample size of 168 patients who are eligible to activate the alert are required in each treatment group, for a total study sample size of 672 patients encounters. We anticipate that we can achieve this number of patient encounters across the approximately sixty participating clinicians including any possible attrition.

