permits the evaluation of prescription rates by groups while controlling for covariates and the correlated and hierarchical effects of repeated measures nested within clusters. Statistical significance of the treatment group and the other covariates will be determined using odds ratio with 95% confidence intervals that do not contain 1.0. For the Secondary RE-AIM Outcomes, the GLMM, with the same random effects specification, will be used to estimate the safety risk for prescriptions of SGLT2 and MRA within 30 days of the nudge interventions and compare this risk between the intervention and control groups. These metrics will be evaluated to estimate the risk of discontinuation of the prescribed medications based on adverse effects. The outcome for this analysis will be the continuation or stoppage of the prescribed medication. The other metrics identified in the secondary outcomes above will be calculated as descriptive statistics and will inform revisions to the interventions.

Qualitative Analysis: To ensure analytic rigor, all analysts have experience in qualitative methods. Data collection and analysis will be conducted concurrently using deductive and inductive content analysis. Transcripts will be uploaded to ATLAS.ti for coding and data management. Coding is conducted using audio recordings and transcriptions simultaneously to ensure transcription fidelity and capture participant inflection not contained in transcript. Deductive content analysis consists of identifying quotes and phrases that fit within pre-identified and defined a-priori categories. A-priori categories include general behavioral economics principles, prism, RE-AIM domains. Inductive content analysis involves open/unstructured coding, and allows for the identification of emergent, previously unidentified and to capture data that did not fit into a-priori categories. For open coding, we will use a three-step process described by Strauss and Corbin to code the data, starting with open codes, followed by axial codes, and ending with theoretical codes (Strauss & Corbin, 1998). Coding will continue until thematic saturation (Sandelowski, 1995).

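### The stoppage (safety) comparison uses a mixed model with patient, clinician and clinic random effects that about one binary result per prescribed patient cannot support, and its only reading rule is whether the odds-ratio CI contains 1.0

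*Combined protocol and SAP*

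**What the plan says.** Section 8.0 (Data Analysis) fits the prescribing outcome with a generalized linear mixed model that has patient, clinician and clinic as random effects. Treatment-group significance "will be determined using odds ratio with 95% confidence intervals that do not contain 1.0". The secondary RE-AIM text then states that "the GLMM, with the same random effects specification, will be used to estimate the safety risk for prescriptions of SGLT2 and MRA". The window is 30 days after the nudge, and the contrast is intervention against control. It adds: "The outcome for this analysis will be the continuation or stoppage of the prescribed medication".

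The power paragraph of the same section concerns prescribing only: "We anticipate a 5% absolute increase in new prescriptions (SGLT2 or MRA) per intervention arm, compared to usual care", and "a sample size of 168 patients who are eligible to activate the alert are required in each treatment group". It gives no expected stoppage rate, safety precision or safety power.

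Section 5.4.2 lists adverse events and mortality among the data collected, but no between-arm analysis is given for them. Section 8.0 makes the other secondary metrics descriptive. Section 7.0 says "These are not experimental therapies, and DSMB is not required". Stoppage is therefore the only modelled between-arm safety comparison.

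**The concern.** A model built for a prescribing outcome, with repeated visits from every eligible patient, is carried over to an outcome that exists only after a prescription and occurs about once per patient. A patient random effect needs repeated results within patients, and these data have almost none. Clinician and clinic effects must be estimated from the same few events. The fit may fail to converge, or may return an odds ratio that depends on a variance the data do not determine.

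The reading rule adds to this. A rule that asks only whether the CI contains 1.0 can return a difference or no significant difference. In so few patients the second answer is likely over much of the plausible range, whether the nudges leave stoppage unchanged or double it. Section 1.1 presents the nudges as scalable across therapeutic areas. A null stoppage result could be taken as reassurance that the data do not provide.

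**Working it through.** **The plan's own figure.** No figure is stated for the safety comparison, so there is none to reproduce. The 168 per group belongs to prescribing (5 points, 80% power, alpha 0.05) and comes without a control rate. With the usual two-proportion formula, two-sided, 168 corresponds to a control rate of only about 0.2-0.35%; at 19% the formula gives 1,059. Here 168 is used only as the planned number of eligible patients per arm.

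**Inputs**
- Eligible per arm: 168 (section 8.0). As a larger case, 1,400 patients for analysis (section 4.2) / 4 = 350, if the arms are equal.
- Usual-care prescribing: not stated. Assumed 10%; 19%, the lower figure of the earlier alert trial in section 1.0; and, for 350 per arm, 22%, which is current SGLT2 use and not a new-prescription rate.
- Nudge arm: usual care plus 5 points (section 8.0).
- Stoppage within 30 days: not stated. Assumed 5%, 10% and 20%.
- Clinicians: about 60 (section 8.0), so about 15 per arm if equal.

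**Step 1. Number prescribed**
- 10% v 15% of 168: 17 v 25.
- 19% v 24% of 168: 32 v 40.
- 22% v 27% of 350: 77 v 95.

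With 15 clinicians per arm, the first two rows give about 1.1 to 2.7 prescribed patients per clinician (17/15 to 40/15).

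**Step 2. Patient random effect.** With one binary result per patient, the data inform only the marginal stoppage risk in each arm. Take 10% v 20%. Solving for the logistic-normal intercepts that give these two risks at a fixed patient SD yields:

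| Patient SD (logit scale) | Odds ratio in the model |
|---|---|
| 0 | 2.25 |
| 2 | 3.3 |
| 4 | 6.9 |

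All three fit the same data equally well. A patient prescribed both drugs could contribute two results if the drugs were analysed together. Separate models by drug, as planned for prescribing, would remove even that.

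**Step 3. No finite odds ratio.** With common stoppage s, P(at least one arm has no stoppage) = (1-s)^n0 + (1-s)^n1 - (1-s)^(n0+n1).
- 17 v 25, s = 10%: 0.167 + 0.072 - 0.012 = 0.23. With s = 5%: 0.58.
- 32 v 40, s = 10%: 0.034 + 0.015 - 0.001 = 0.05. With s = 5%: 0.30.

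**Step 4. Missing a doubling.** Exact binomial enumeration with a Wald 95% CI for the log odds ratio, 0.5 added to each cell, one nudge arm v usual care, drugs pooled, no clustering. Probability that the CI contains 1.0:

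| Prescribed | 5% v 10% | 10% v 20% | 20% v 40% |
|---|---|---|---|
| 17 v 25 | over 99% | 98% | 79% |
| 32 v 40 | 99% | 88% | 59% |
| 77 v 95 | 85% | 61% | 19% |

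For scale, 80% power for 10% v 20% needs (1.96 + 0.84)^2 x (0.10 x 0.90 + 0.20 x 0.80) / 0.10^2 = about 197 prescribed patients per arm, more than the 168 eligible.

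**The case against.** **The miss rates rest on assumed rates.** This is correct. The documents give neither a stoppage rate nor a control prescribing rate. A reader might infer that the design misses a doubling at least three times in four. That holds across 10-60 prescribed per arm only if control stoppage is below about 9%. At 20% stoppage the miss rate is 59% for 32 v 40 and 19% for 77 v 95. Nor is 168 a cap, since section 8.0 analyses all eligible dashboard patients.

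**The CI rule reaches safety only by inheritance.** This also stands. The rule closes the description of the prescribing model, and the safety sentences speak of estimating and comparing risk. A reader might infer that the plan treats a non-significant result as safe; it says no such thing. A reported CI would also show its upper limit. But no other reading rule is given, and nothing says how that limit will be interpreted.

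**The covariates.** Only the random effects are expressly carried over. It is tempting to say that the stoppage model also has the five prescribing covariates, but the text does not say so, and the point does not need it.

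**Context.** Aim 2 is preliminary, the trial has one site, and stoppage is a secondary outcome for guideline-recommended drugs. Serious adverse events go to the IRB (section 10.3). Leaving such an outcome unpowered and without a formal margin is usual. So the absence of a margin or of safety power is not in itself an error, and no claimed safety power is missed.

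None of this rescues a patient random effect fitted to about one result per patient.

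**Conclusion.** The concern holds as a fault in a stated analysis. Non-identification of the patient variance follows from the data structure and needs no assumed rate: with one result per patient, 10% v 20% stoppage is equally an odds ratio of 2.25, 3.3 or 6.9. The other sizes are conditional on the assumed prescribing and stoppage rates. With 168 eligible per arm, no finite odds ratio arises in about 5-23% of comparisons at 10% stoppage in both arms and 30-58% at 5%. A doubling is missed about 88-98% of the time from 10% and 59-79% from 20%. With 350 eligible per arm the miss rates are about 61% and 19%. Clustering is ignored, so these miss rates are if anything too low; separate models by drug would raise them further.

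The documents do not support a single miss rate as a property of the design, or a claim that the plan equates non-significance with safety. The change is worth making because it is cheap and the present model is unsound for this outcome.

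**What to change.** In the secondary-outcome text of section 8.0:

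1. Replace the three-random-effect model for stoppage with an arm-only analysis that allows for clinician clustering: a clinician-level summary, or a penalised (Firth-type) logistic model with clustered inference.
2. For each nudge arm v usual care, report the number prescribed, the number who stopped, and the absolute risk difference with its 95% CI.
3. Read the result from the interval and its upper limit, not from whether an odds-ratio CI contains 1.0. State that the comparison is not powered, and that an interval including no difference is inconclusive, not evidence of no excess stoppage.
4. Note that the contrast is among patients selected by prescribing, which happens after randomisation and which the nudges are meant to change, so it is not a fully randomised comparison.

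A formal margin is optional. If one is used, the investigator should fix it before outcome data are examined; the documents describe no blinding.

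The cost is a wording change and a simpler analysis, with no extra patients, data or staff. The downsides are a less favourable safety statement, probably inconclusive, and no covariate adjustment for this outcome. The change does not add information; it stops the result from being read as more than it is.

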Data Analysis. Though randomization occurs at the clinician level, we will measure outcomes at the patient level. The dataset used for analysis will be limited to all MRA- and SGLT2i-eligible identified in the HF dashboard (this includes patients in the control group-- even though no alert will be generated). This sample allows us to compare differences in rate of prescription of the same patient types between the three intervention groups and control group. Descriptive statistics will comprise patient and provider demographics, including practitioner specialty and type, and part-time status. General Linear Models (GLM) and chi square tests will be used to compare continuous and categorical demographic variables, respectively, between the three interventions and control groups. Significant differences will be defined with p values < 0.05. Generalized Linear Mixed Models (GLMM) will be used to compare rates of both SGLT2 or MRA (in separate, univariate analyses) between the nudge intervention and control groups. Practitioner specialty and type, part time status, years of experience, and patient visit number will be included as covariates, and the patient, clinician, and clinic assignment (clustering of providers), will be entered as random effects. While these covariates are strata for randomization, it is unlikely, due to the study sample size, that all combinations will be equally distributed between the two groups. We will therefore need to employ statistical control of these potential influences. The GLMMs will be specified as random coefficient models or growth curve models to evaluate changes in prescription behavior over time, as well as between groups. Models will include the preintervention baseline as a covariate and will use all patient visits until the conclusion of the data collection period. Significant differences will be concluded with odds ratio and 95% confidence intervals that do not contain the value 1.0. This statistical approach

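### The drug-stoppage model inherits a patient random effect that cannot be estimated if each patient gives one result per drug, so the software, not the data, sets the size of the safety odds ratio

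*Combined protocol and SAP*

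**What the plan says.** Section 8.0 sets up the prescribing model first. In it, "the patient, clinician, and clinic assignment (clustering of providers), will be entered as random effects". A patient can supply several rows there, because the models "will use all patient visits until the conclusion of the data collection period", and the section justifies the structure by repeated measures within clusters. The two drugs are handled in separate models: the mixed models "will be used to compare rates of both SGLT2 or MRA (in separate, univariate analyses").

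The same section then turns to the secondary RE-AIM outcomes and states that "the GLMM, with the same random effects specification, will be used to estimate the safety risk". The aim is to "estimate the safety risk for prescriptions of SGLT2 and MRA within 30 days of the nudge interventions", compared between intervention and control groups. The endpoint is binary: "The outcome for this analysis will be the continuation or stoppage of the prescribed medication". Inference follows the rule given for prescribing: "Significant differences will be concluded with odds ratio and 95% confidence intervals that do not contain the value 1.0". The remaining secondary metrics are descriptive, so this is the only safety comparison with a model.

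For the safety model the plan does not say what a row is (patient, prescription or visit), whether the two drugs are pooled, or what happens if a variance component cannot be estimated.

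**The concern.** A patient random intercept describes correlation between several results from the same person. Repeated visits provide that for prescribing. They do not obviously provide it for stoppage, where a started drug is either continued or stopped within the window. With one binary value per patient in each drug's model, nothing in the data separates between-patient variance from the fixed effects: a larger variance with proportionately larger coefficients fits equally well. The fit may then fail, return a zero variance, or run to a boundary.

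What is at stake is the size of the estimate. The stated purpose is to estimate a risk. With few stoppages the test will probably be inconclusive, and readers will then look to the odds ratio and its interval. Those are the quantities that depend on the unidentified variance.

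**Working it through.** **Inputs.** The plan gives no stoppage rate, number of prescribed patients or patient variance for this model. Its only sample-size statement ("To detect this difference with an 80% power and alpha of 0.05, a sample size of 168 patients" per group) concerns prescribing, so there is no planned safety figure to reproduce. Assumed for illustration: stoppage 10% (control) versus 20% (intervention), 40 prescribed patients per arm (4/40 and 8/40), one row per patient, and patient SD s from 0 to 5.

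**Step 1: the likelihood.** Let logit P(stop | u) = b_arm + u, with u ~ N(0, s²). With one row per patient the data enter only through the marginal probability π_arm = E[expit(b_arm + sZ)], Z standard normal. For any s, b_arm can be solved so that π_arm equals the observed proportion. The maximum is therefore the same for every s:

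4 ln 0.1 + 36 ln 0.9 + 8 ln 0.2 + 32 ln 0.8 = -9.210 - 3.793 - 12.876 - 7.141 = -33.02.

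**Step 2: the odds ratio.** Conditional OR = exp(b1 - b0). By the delta method, SE² = Σ π(1-π)/(n D²), summed over the two arms, with D = E[expit'(b + sZ)]. Expectations are by Gauss–Hermite quadrature.

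| Patient SD | b0 | b1 | OR | 95% CI | z | Max. log-likelihood |
|---|---|---|---|---|---|---|
| 0 | -2.197 | -1.386 | 2.25 | 0.62 to 8.2 | 1.23 | -33.02 |
| 1 | -2.564 | -1.650 | 2.50 | 0.59 to 10.6 | 1.24 | -33.02 |
| 2 | -3.417 | -2.228 | 3.28 | 0.51 to 21 | 1.25 | -33.02 |
| 3 | -4.472 | -2.929 | 4.68 | 0.41 to 53 | 1.25 | -33.02 |
| 5 | -6.810 | -4.470 | 10.4 | 0.26 to 409 | 1.25 | -33.02 |

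The data cannot choose between these rows. The coefficient and its standard error grow together, so z hardly moves.

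**Step 3: other assumed rates** (25 control and 75 intervention patients, SD 0 to 5).

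| Stoppage | OR | z |
|---|---|---|
| 10% v 20% | 2.25 to 10.4 | 1.12 to 1.16 |
| 5% v 10% | 2.11 to 6.93 | 0.75 to 0.78 |
| 10% v 15% | 1.59 to 3.69 | 0.62 to 0.64 |

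**Step 4: does a covariate rescue it?** In 40 simulated datasets (150 patients, true SD 1, one continuous covariate, no clinician effect), the SD was profiled over a grid from 0 to 6. With one row per patient the median range of the profile log-likelihood was 0.03, and the estimate fell at an end of the grid in 34 of 40 datasets (17 at 0, 17 at 6).

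**Step 5: what if some patients give two rows?** With 40% of patients giving two rows in the same simulation, the median range was 13.0 and the estimate lay between 0 and 2 in all 40 datasets (12 of them at 0). A smaller pooled setting (25 control and 75 intervention patients, true SD 1, no clinician effect, 90 of 100 datasets usable) gave:

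| Patients with two rows | SD estimate on the boundary | Median fold-range of OR over SDs within 1.92 log-likelihood units of the best fit |
|---|---|---|
| 10% | 56 of 90 | 2.5 |
| 20% | 42 of 90 | 1.9 |
| 40% | 29 of 90 | 1.5 |

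**Step 6: what an approximate fit might do.** For 4/40 versus 8/40, a Laplace approximation does not stay flat. Its log-likelihood rises from -33.0 at SD 0 to -21.2 at SD 12, so it favours ever larger SDs. Its odds ratio nevertheless stays between 2.25 and about 2.9.

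**The case against.** The strongest objection is to the premise. Nowhere does the plan say that stoppage is one row per patient, or that the drugs are modelled separately for safety. The separate-models statement belongs to prescribing, the safety sentence names both drugs together, and the prescribing text speaks of all visits. Under a pooled or visit-level dataset some patients give several rows, and Step 5 shows that the variance then becomes estimable. This stands: one value per patient and drug is an inference, though the natural one for a stop/continue endpoint. It does not dispose of the point, because with few double starters the variance remains poorly determined, and the plan does not say how many to expect.

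The second objection is to the consequence. A reader might infer that the safety result is arbitrary, or that the same counts could well be published as an odds ratio near 10. The documents and the arithmetic do not support that. The plan's rule is an interval excluding 1, and that conclusion is almost unaffected. An odds ratio of 10.4 needs SD 5, a latent within-patient correlation of 25/(25 + 3.29) = 0.88, and it would carry an interval of 0.26 to 409. A failed fit yields no estimate, a zero variance yields the ordinary 2.25, and the Laplace fit stayed below 3. This objection also stands.

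Third, the argument says nothing against the clinician or clinic effects or the covariates. Clinicians and clinics can contribute several patients. Agreed: reducing the covariates is no part of this point.

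**Conclusion.** The point holds in a limited form. Section 8.0 instructs the analyst to carry a patient random effect, justified by repeated visits, to an outcome that on its natural reading has no repetition within patient. The exact likelihood is then flat in the patient SD. The size of the conditional odds ratio and the width of its interval depend on how the software handles that, over a possible range of 2.25 to 10.4 in the main illustration. Direction, z and the interval-excludes-1 conclusion are essentially stable.

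This rests on one row per prescribed patient and drug, which the plan implies but does not state, and on assumed stoppage rates and numbers. Under pooling or visit-level rows it weakens to a variance that can be estimated but perhaps only poorly. Because the analysis is secondary and its test conclusion is robust, this should be corrected but does not threaten the trial. It matters because this is the only modelled safety comparison and its purpose is estimation.

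**What to change.** In Section 8.0, replace the clause that reuses the prescribing model's random effects with a specification for stoppage:

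- one row per prescribed patient and drug;
- no patient random effect;
- clinician-level clustering retained, and clinic as well if it can be estimated;
- for each arm, the number prescribed and the number stopped, and a risk difference against control with its interval, alongside the odds ratio.

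In the 4/40 versus 8/40 illustration, ignoring clustering, the risk difference is 10 points with SE = √(0.09/40 + 0.16/40) = 0.079, so the interval is -5.5 to 25.5 points. It does not depend on any patient variance.

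If SGLT2 and MRA are to be pooled, the plan should say so and state that the patient effect is dropped when its variance is on the boundary.

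The cost is a few sentences, submitted for approval as Section 10.1 requires for amendments. Section 5.4.2 already collects new prescriptions and discontinuations, so no extra data, patients or time are needed.

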
Your patient has been identified in VA HF Dashboard as potentially eligible for an SGLT2 inhibitor. This alert is provided for informational purposes.
 
SGLT2 inhibitors are indicated in the 2022 ACC/AHA HF Guidelines (URL link provided) for patients with HFrEF (EF≤40%, NYHA class II-IV HF). Contraindications include urinary tract infection, eGFR < 25, type I diabetes.
 
Relevant data for this patient include: Prescription for beta blocker No prescription for ACE inhibitor LVEF 40% BNP 1550 Renal function: eGFR > 25
 
Suggested actions: Prescribe empagliflozin 10mg daily Alert primary care
 
If prescribing: Recommend checking renal function after starting therapy; reduce diuretic; watch for dehydration
	
Dear Dr. _____,
 
SAVAHCS Cardiology is working on new ways to help clinicians improve their patient's HF treatment. Based on AHA/ACC guidelines and the VA HF Dashboard, you have patients who could be on an SGLT2 inhibitor but have not been prescribed one.
 
Among eligible patients, your rolling 90-day SGLT2 prescribing rate: XX% [one of the following] Average of your peers at SAVAHCS: XX% Your top performing peers at SAVAHCS: XX%
 
If you have any questions, please email study coordinator XXX
 
Sincerely, XXXX Clinical Research Coordinator XXXX Study Principal Investigator

Focus group with SAVAHCS Veteran and Family Advisory Council

[figure not shown]
We will meet twice virtually with the Advisory Council during the study. We will ask for their feedback on their perceptions of study benefit and any suggestions for improvement. Unlike the other focus groups and interviews with clinicians, we will only take notes, but no audio

recording will occur. We will not ask for any individually identifiable information, only general feedback on the study.

Aim 2. NUDGE EFFECTIVENESS

Table 2. Study design			
	Peer comparison		
		Yes	No
Informational alert	Yes		
	No		

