5.4.2 SUBJECT EVALUATIONS

Aim 1.

Subject	Data	Data source
Clinician	Verbal feedback: nudge intervention, workflow Quantitative measures of intervention suitability: questionnaires (Acceptability, Appropriateness, Feasibility) & Clinician general demographics: sex, practice site, specialty/subspecialty, and percent full-time effort, years of experience	Interview, focus group (see attached Interview Guides) Questionnaires (administered via VA Redcap)
Veteran and Family Advisory Panel	Feedback on intervention, workflow	Focus Group

Aim 2.

Subject	Data	Data source
Patient (12 months before baseline, during and post-nudge)	Name, full SSN, dates, demographics, vitals, zip-code level median household income, clinical encounters, Charlson Comorbidity Index, and medications; # alerts delivered, # new HF prescriptions (MRA or SGLT2), # HF	CPRS, HF Dashboard, CDW/VINCI

	medication discontinuations, adverse events, mortality	
--	--	--

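### The safety model targets stops due to adverse effects but analyses stoppage with no cause attached, and no between-arm comparison of adverse events or deaths is specified

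*Combined protocol and SAP*

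**What the plan says.** Section 8.0 (Data Analysis, secondary RE-AIM outcomes) applies the mixed model used for prescribing to a safety question. The scope of that safety model is worded as follows: "prescriptions of SGLT2 and MRA within 30 days of the nudge interventions and compare this risk between the intervention and control groups". The purpose is then given as to "estimate the risk of discontinuation of the prescribed medications based on adverse effects", and the variable to be modelled is named in the next sentence: "The outcome for this analysis will be the continuation or stoppage of the prescribed medication".

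The Aim 2 table in Section 5.4.2 lists the patient-level items that bear on this: "medication discontinuations, adverse events, mortality". They are separate items, and a reason for stopping is not among them.

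On everything else in the secondary set, Section 8.0 says: "The other metrics identified in the secondary outcomes above will be calculated as descriptive statistics and will inform revisions to the interventions". The list that this sentence points back to is not in the text available for this review.

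Three other places matter. Section 5.3 admits patients who are not already on the drug class. Section 8.0 keeps control-group patients in the analysis set although no alert is generated for them. The consent table in Section 5.2 allows outcome review up to 90 days after nudge delivery, whereas the safety sentence in Section 8.0 refers to 30 days.

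**The concern.** The target and the variable are not the same quantity. A drug may be stopped because of an adverse effect, patient preference, a switch or a lapse in renewal. Scored as continued or stopped, all of these count alike, while an adverse event managed without stopping the drug counts as a continuation. The text does not say how a death is scored.

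This matters because it is the only safety comparison between arms that the available text specifies. Section 7.0 plans no data monitoring board. A difference in stoppage could be read as a difference in harm, or its absence as reassurance, when neither follows.

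**Working it through.** **Step 1. Is there a figure to reproduce?** No. The documents give no stop rate, margin, sample size or power for this outcome. The check is a comparison of the texts, followed by arithmetic on assumed rates.

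**Step 2. Texts side by side.**
- Stated target (Section 8.0): stops caused by adverse effects.
- Variable modelled (Section 8.0, next sentence): continued or stopped.
- Data collected (Section 5.4.2): discontinuations, without a reason.
- Attribution rule, person who attributes, handling of switches, lapses and deaths: not found in any section.

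The stated target therefore cannot be computed from the listed data by the described model.

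**Step 3. How far can the proxy depart from the target?** Among patients started on the drug, treating the two kinds of stop as exclusive:

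P(any stop) = P(adverse-effect stop) + P(other stop), and odds ratio = [p1/(1−p1)] / [p0/(1−p0)].

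The odds ratio is used because it is the plan's own measure. All rates below are assumptions; clustering and covariates are ignored.

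| Adverse-effect stops, control v nudge | Other stops, control v nudge | Any stop, control v nudge | True OR (adverse-effect stops) | OR from any stop |
|---|---|---|---|---|
| 5% v 10% | 5% v 5% | 10% v 15% | 2.11 | 1.59 |
| 5% v 10% | 10% v 10% | 15% v 20% | 2.11 | 1.42 |
| 5% v 10% | 15% v 15% | 20% v 25% | 2.11 | 1.33 |
| 5% v 10% | 10% v 5% | 15% v 15% | 2.11 | 1.00 |
| 5% v 5% | 5% v 10% | 10% v 15% | 1.00 | 1.59 |

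Worked example, first row: (0.10/0.90)/(0.05/0.95) = 2.11, and (0.15/0.85)/(0.10/0.90) = 1.59. The first three rows dilute the effect, the fourth hides it, and the fifth creates one where none exists.

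**Step 4. Who can have the outcome?** Eligible patients are not on the drug at entry, so only those newly prescribed it can stop it. Raising new prescriptions is the purpose of the nudges, so the starters are a subset formed after randomization, and one that the intervention alters. A comparison among them is not protected by randomization.

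**Step 5. How many starters?** Take the planned 168 patients per arm (Section 8.0) and assume that 5% to 22% start a drug under usual care:
- usual care: 168 × 0.05 = 8.4 to 168 × 0.22 = 37.0;
- with the plan's anticipated 5-point gain: 168 × 0.10 = 16.8 to 168 × 0.27 = 45.4.

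With 8 to 45 starters in each arm, a two-sided 5% test of 5% v 10% stopping has power of about 6% to 14% (normal approximation, rough at such counts, no clustering). About 435 starters per arm would be needed for 80%.

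**Step 6. From when is the window counted?** Alerts are tied to an appointment (Section 4.3). Peer-comparison emails go to the clinician about every two weeks and are not tied to a patient. Control patients have no nudge at all. A window counted from the nudge therefore has no patient-level start date in control, and none is defined in the email-only arm.

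**The case against.** The strongest reply is that the two sentences are adjacent, and the second may simply be the binary coding of the quantity just named. On that reading nothing is defined as all-cause. This stands in part: the text is ambiguous and does not expressly call for stops for any reason. It does not rescue the plan, because the narrower reading needs a cause for each stop, and neither a cause field nor an attribution rule is given.

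A second reply is that harm data are collected and that the remaining secondary metrics are to be described. That also stands. Since the list referred to is not in the available text, it cannot be said that adverse events and deaths go unreported, only that no comparison between arms is specified for them.

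Third, this is a secondary outcome in an evaluation that Section 2.0 calls preliminary, and the starters are few. That limits the practical effect and argues for estimation over testing, but not for leaving the target and the variable different.

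A reader might go further in three ways that the documents do not support.
- *That a stop is the nudged clinician's decision, discouraged by the peer email.* No section says who stops a drug; it could be the patient, another clinician or a pharmacist. The email prototype shows "Among eligible patients, your rolling 90-day SGLT2 prescribing rate", but nothing says that stopping a drug lowers the displayed figure.
- *That the outcome does not measure harm at all.* Adverse-effect stops are a subset of stops, so it is a non-specific proxy, not an irrelevant one.
- *That potassium and renal function should become safety endpoints,* because Section 8.0 says that "MRAs require serial lab monitoring". The alert prototype in Section 4.3 itself prompts renal testing after a start, so abnormal values could be found more often in the alert arms without any excess harm. The eGFR figures also differ (25 in the alert text, 20 in Section 5.3) and must be reconciled before either could serve as a threshold.

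**Conclusion.** The concern holds in this form: as written, the safety model does not estimate its stated target. All-cause stoppage can dilute, hide or mimic a difference in harm. The illustration moves a true odds ratio of 2.11 to anywhere from 1.59 to 1.00, and a true 1.00 to 1.59. These figures rest wholly on assumed stop rates; the documents do not allow the actual size or direction of the error to be found. Two further weaknesses come from the documents themselves: the outcome exists only in a subset that the nudge changes, and its 30-day window has no defined start in every arm. The absence of a specified comparison of adverse events and deaths is a statement about the available text only. The point should be put right before analysis. It does not touch the prescribing endpoint.

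**What to change.** 1. In the chart review already planned, record the reason for each stop (adverse effect or other) by a written rule applied without knowledge of arm. The rule should say how a switch, a lapsed renewal, an undocumented reason and a death are handled. Use adverse-effect stops for the stated target.
2. Report all-cause stoppage separately, labelled as persistence and not as safety.
3. Specify a between-arm comparison of the adverse events and deaths already collected, among all eligible patients in every arm including control. Use one window starting from an index visit that exists in all arms, for example the first eligible appointment in the intervention period. Reconcile the 30 days in Section 8.0 with the 90 days in Section 5.2.
4. Give these results as estimates with confidence intervals, since events will be few.

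The cost is a small amount of extra chart coding for a limited number of stops, plus revised wording in Sections 5.4.2 and 8.0. Two limits remain. Precision will be low whichever outcome is used. Masking the coder also cannot remove any influence of the nudge on what treating clinicians write in the chart, which is a further reason to put the comparison in item 3 beside the coded stops.
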